8.2 Statistical methods

Hypothesis testing

Formal testing of the 1st primary hypothesis claiming a difference of 20% or more for speech understanding will be carried out by using a paired t-test on differences of speech understanding (i.e. values at visit 6 months - values at pre-op) with a reference proportion of 20%. Number of patients with values greater or less than 20% will be reported.

Formal testing of the 2nd primary hypothesis claiming an improvement of 80% or more of patients showing post-operative improvement will be carried out by using a binomial test (one-sample) of improvement rates with a reference proportion of 80%.

These tests will be carried out at the final analysis only. For interim analyses, descriptive rates along with 95% confidence levels will be produced reporting the frequencies of responses along with the 95% CI based on exact methods (Clopper-Pearson) for visits pre-op, month 3 and month 6.

At the final analysis, in addition refined analyses will be carried out based on a modeling approach. This enables a more sensitive analysis allowing for covariates (such as baseline characteristics). Regression analyses will be carried out for this purpose incorporating the paired structure of observations. To this end the SAS proc genmod will be used (procedure glimmix will be used as a sensitivity analysis as it estimates random effects using a different approach). Furthermore, this modelling approach allows for:

- estimating consolidated treatment effects comparing post-baseline vs. pre-op performance.
- considering center specific deviations from the thresholds used by keeping these threshold as covariate for the binomial response (success rate).

Analyses will be carried out both based upon the ITT population and the PP set. Due to the nature of the data, i.e., paired data analyses based upon ITT, this will be considered as secondary and carried out in the perspective of a sensitivity analysis. For this purpose a random effects model is required to be used treating the patient as random effect.*.

* Brown, H. & Prescott, R. (1999). *Applied Mixed Models in Medicine*, New York: John Wiley & Sons.

Analyses based on continuous outcomes such as audiometric thresholds or electrode impedances will be carried out in a similar manner using the SAS proc mixed to account for random effects of normally distributed data.

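### SAP 8.2 justifies PROC GLIMMIX as a check on PROC GENMOD as if both estimated random effects; GENMOD fits none, so their odds ratios can differ with nothing amiss, and the binary ITT random-effects model has no named procedure

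*SAP*

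**What the plan says.** SAP section 8.2 sets out two formal tests, a paired t-test and a one-sample binomial test. It then adds the models at issue: "At the final analysis, in addition refined analyses will be carried out based on a modeling approach". Their form is given as follows: "Regression analyses will be carried out for this purpose incorporating the paired structure of observations". The procedure is named next: "To this end the SAS proc genmod will be used". A parenthesis gives the check and its reason: "procedure glimmix will be used as a sensitivity analysis as it estimates random effects using a different approach". One listed use of the models is "considering center specific deviations from the thresholds used by keeping these threshold as covariate for the binomial response (success rate"), so the response is binary.

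A later paragraph of 8.2 covers the analysis sets. Of the ITT analysis it says that "this will be considered as secondary and carried out in the perspective of a sensitivity analysis", and then: "For this purpose a random effects model is required to be used treating the patient as random effect". That sentence names no procedure. Continuous outcomes are sent separately to PROC MIXED.

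Three other sections matter:

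- SAP 5 defines the binary response as better, versus worse or equal, relative to pre-op.
- SAP 7 defines ITT as every patient with a baseline assessment, and PP as patients with pre-op plus month 3 or month 6.
- SAP 8.1 treats the visit effects (month 3 and month 6, each against pre-op) as the treatment effects to be tabulated.

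The SAP gives no link function, working correlation or GLIMMIX estimation method, and does not say that effects will be reported as odds ratios.

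**The concern.** The reason given for GLIMMIX makes sense only if GENMOD also estimates random effects. It does not. This is general knowledge of the software and is not stated in the documents. GENMOD accounts for repeated observations by GEE: a marginal model with a working correlation, whose coefficients compare population averages. GLIMMIX with a patient random intercept compares outcomes within a patient. On the logit scale these are different parameters, and the patient-specific one lies further from 1 whenever patients vary and there is an effect.

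Two things are at stake. First, a difference in the size of the two odds ratios would be read as lack of robustness when it is expected by construction. Second, someone programming the binary ITT analysis finds GENMOD as the main procedure, a required model that GENMOD cannot fit, and no statement of what to use. SAP 4 allows validation by reprogramming from the SAP, and two programmers could reasonably diverge here.

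**Working it through.** **Inputs.** The SAP gives no figure for the GENMOD or GLIMMIX models. Its only paired binary scenario is Table 2 in SAP 2.1: proportions p1 = 0.5 and p2 = 0.7, within-patient correlation rho = 0.5, 150 pairs, two-sided alpha 0.05. A logit link and a normal patient intercept are assumed.

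**Table 2 reproduced.** Cell probabilities, with the first index for pre and the second for post:

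- p11 = p1·p2 + rho·√(p1·q1·p2·q2) = 0.35 + 0.5 × √(0.25 × 0.21) = 0.4646
- p10 = 0.5 − 0.4646 = 0.0354
- p01 = 0.7 − 0.4646 = 0.2354
- p00 = 0.2646

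Summing the exact conditional McNemar test over the number of discordant pairs gives power 0.981, 0.995 and 0.999, with actual alpha 0.0300, 0.0322 and 0.0348, at 100, 125 and 150 pairs. These match the printed table.

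**Population-averaged odds ratio (the GEE target).** (0.7/0.3) / (0.5/0.5) = 2.33.

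**Patient-specific odds ratio (the random-intercept target).** For two observations per patient this equals p01/p10 exactly, because the intercept cancels from that ratio within each patient. From unrounded cells, 0.23544 / 0.03544 = 6.64. A random-intercept logistic model solved to the same margins and correlation returns the same 6.64, with an intercept SD of 3.15. The same data thus give two correct answers that differ by a factor of 6.64 / 2.33 = 2.8.

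**Dependence on rho** (margins held at 0.5 and 0.7):

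| rho | population-averaged OR | patient-specific OR |
|---|---|---|
| 0 | 2.33 | 2.33 |
| 0.1 | 2.33 | 2.57 |
| 0.3 | 2.33 | 3.46 |
| 0.5 | 2.33 | 6.64 |
| 0.6 | 2.33 | 16.97 |

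**Simulation.** In 300 simulated trials of 150 pairs from the rho = 0.5 cells, the median odds ratio was 2.36 by GEE and 7.00 by random-intercept maximum likelihood.

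**A second illustration, on assumed values only.** With a patient-specific odds ratio of 3.0, an intercept of 1.5 and a random-intercept SD of 1, 2 or 3, integrating over the intercept gives population-averaged odds ratios of 2.64, 2.04 and 1.69.

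**Direction and significance** (Table 2 inputs, n = 150):

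- Population-averaged: ln 2.333 = 0.847. Variance = [1/0.25 + 1/0.21 − 2 × 0.5/√(0.25 × 0.21)] / 150 = (4 + 4.762 − 4.364) / 150 = 0.0293, so SE = 0.171 and z is about 4.9.
- Patient-specific: ln 6.644 = 1.894. Variance = 1/(150 × 0.2354) + 1/(150 × 0.0354) = 0.0283 + 0.1881 = 0.2165, so SE = 0.465 and z is about 4.1.

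The inference is the same; only the effect size differs.

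**Which outcome can carry the ITT model.** The response in SAP 5 is itself a change from pre-op, so it has no pre-op value. Used at month 6 only, it gives one value per patient and a patient random effect cannot be identified. Used at months 3 and 6, it leaves out patients with a baseline and no follow-up, so the ITT set of SAP 7 shrinks to the PP set, and it gives no contrast with pre-op of the kind SAP 8.1 asks for. An outcome scored at each visit, pre-op included, avoids both problems.

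**The case against.** The strongest reply is that this is a wrong parenthesis in a supplementary analysis. The regressions come on top of the formal tests, GLIMMIX is a sensitivity analysis, and ITT is secondary. That stands, and it sets the severity.

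The size of the gap also depends on choices that the SAP leaves open. It states neither a link nor an odds ratio, and a GLIMMIX fit with residual-side covariance only would target the marginal parameter. The 2.33 versus 6.64 contrast uses Table 2's pre/post binary outcome, not the change response of SAP 5. These limits stand as conditions on the figures. They do not rescue the stated reason for GLIMMIX, and the SAP's wording points to random effects.

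Nor is the comparison worthless. In a random-intercept logit model one odds ratio is 1 exactly when the other is, so agreement on direction and significance does carry information.

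Three stronger readings are tempting, and the documents do not support them:

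- **That GENMOD is assigned to the ITT analysis.** The sentence requiring random effects names no procedure. Section 8.2 can be read as GEE for the main regressions and a mixed model for ITT. The fault there is an omission.
- **That ITT differs from PP by keeping patients with month 3 but no month 6.** The PP set keeps them too. ITT adds only patients with no post-operative value.
- **That the SAP meant to avoid a particular missing-data assumption.** It states no such aim.

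**Conclusion.** The concern holds in limited form. The reason SAP 8.2 gives for GLIMMIX is wrong, because GENMOD estimates no random effects. Given a logit link and a patient random intercept, the two procedures estimate different parameters, and a difference in the size of their odds ratios is not evidence of sensitivity. Under the Table 2 inputs that difference is 2.33 against 6.64. It vanishes at zero within-patient correlation and grows with it. Separately, the required random-effects model for the binary ITT analysis has no named procedure, and the response defined in SAP 5 cannot serve it.

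Severity is minor. The paired t-test, the exact binomial test, all three power tables and the PROC MIXED analyses are unaffected. What is affected is the reading of regression estimates that SAP 8.1 will tabulate and that SAP 3 offers as a complement to the binomial test.

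**What to change.** In SAP 8.2:

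1. Describe GENMOD as a population-averaged GEE model, state its link and working correlation, and delete the rationale implying that it estimates random effects.
2. Name PROC GLIMMIX with a patient random intercept and quadrature (METHOD=QUAD) for the binary ITT random-effects analysis. Apply it to a binary outcome defined at each visit, including pre-op, so that baseline-only patients contribute and the visit contrasts of SAP 8.1 can be estimated. Add the definition of that outcome to SAP 5.
3. Compare the two procedures only on a common scale: population-averaged response proportions per visit, with the GLIMMIX predictions averaged over the random effect. Do not compare their odds ratios.

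The cost is a few sentences in the SAP and minor programming. No sample size, formal test or data collection changes.

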3 CONDUCT OF STATISTICAL ANALYSIS

The statistical analyses including reformatting datasets and derivation of outcomes data-management will be carried out by numerics data gmbh, [REDACTED] (i.e. subcontractor).

The speech understanding data will be collected as % correct for either in-quiet or in-noise environments, or speech reception threshold in dB SNR for an in-noise environment.

Electrode location due to proximity to the modiolus, along with duration of deafness and age at onset of hearing loss, will be used as potential variables for the speech understanding. Therefore different categories will be implemented separating patients with a duration of ≤ 30 and > 30 years of age; onset of hearing loss at ≥ 5 and < 5 years of age, close proximity to the modiolus and distanced from the modiolus at the basal turn.

The primary hypothesis will be tested using a one sample (paired) t-test with the difference of the 6 month values versus the baseline values as outcome. This will be done for % speech understanding and dB threshold values. Results will be reported with mean and a 95% CI. The analysis will also be complemented by an analysis of covariance approach, that is, the pre-treatment values are treated as covariate while the values at month 6 are treated as outcome variable. This allows for a sensitive approach to account for baseline covariates such as age, gender and clinic, enabling meaningful average

estimates for specific subgroups with the aim to explore whether the treatment effects hold for the whole study population or are restricted to specific subgroups only. Least squares mean differences are calculated for this purpose.

The secondary hypothesis will be examined using a binomial exact test with a $p=0.8$ as H_0 reference level. This rather crude test will be complemented by regression analyses as described in section 8.2.

The analyses will be carried out with the SAS software (SAS Version 9.4, SAS Institute, Cary, NC, U.S.A.).

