8 EFFICACY ANALYSIS

8.1 Tables, figures and lists

Demographic section

Age and gender distribution by center and overall.

Efficacy outcomes

Descriptive tables of the various outcome variables in the format described under chapter 6 Presentation of data.

Specific tables summarizing the results of the regression analysis (see section below) with estimates +/- standard error of the time effects (visits) and covariates.

Note that time effects will be considered as treatment effects (visit 3 and visit 6 against visit pre-op).

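### The SAP's three-visit models for continuous outcomes name only a patient random effect and no covariance structure, so the 6-month versus pre-op interval may be miscalibrated, probably too narrow

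*SAP*

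**What the plan says.** The formal comparison for primary hypothesis 1 uses two visits only: a "paired t-test on differences of speech understanding (i.e. values at visit 6 months - values at pre-op" (SAP section 8.2). For this test SAP section 3 adds: "Results will be reported with mean and a 95% CI". Section 3 also plans an ANCOVA with month 6 as outcome and the pre-op value as covariate.

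Beyond that, section 8.2 plans regression models. For the refined analyses it says: "To this end the SAS proc genmod will be used (procedure glimmix will be used as a sensitivity analysis". For the ITT population it states that "a random effects model is required to be used treating the patient as random effect", and of that analysis that "this will be considered as secondary and carried out in the perspective of a sensitivity analysis". Continuous outcomes follow in one sentence: analyses of "audiometric thresholds or electrode impedances will be carried out in a similar manner using the SAS proc mixed", the stated purpose being "using the SAS proc mixed to account for random effects of normally distributed data".

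Three visits enter these models. Section 8.1 says: "Note that time effects will be considered as treatment effects (visit 3 and visit 6 against visit pre-op". Protocol section 8.1 confirms that speech understanding and aided and unaided thresholds come from pre-op, 3 months and 6 months.

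Neither document gives a within-patient covariance structure, a random slope, or a choice between model-based and empirical standard errors. Section 8.2 ends by promising residual diagnostics, with no rule for changing the covariance if they look poor.

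**The concern.** With patient as the only random effect and PROC MIXED's default independent residuals, the model assumes equal variance at every visit and equal correlation between every pair of visits. It then applies one pooled variance to every visit contrast.

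The design gives reason to doubt that assumption. Under Protocol section 8.2 the pre-op condition may be unaided, one or two hearing aids, or a unilateral CI, while both post-op visits come after CI532 implantation. Months 3 and 6 may well be more alike than either is with pre-op. The small month 3 to month 6 variance then dilutes the pooled value, and the 6-month versus pre-op standard error is too small.

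At stake are the intervals and p-values of two analyses: the ITT sensitivity model where the speech score is continuous, and the analysis of secondary endpoint 1, for which PROC MIXED is the only inferential model stated.

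**Working it through.** **Inputs from the SAP.** n = 150 and two-sided alpha 5% (section 2). From the earlier OLSA study in section 2.1: SD 3.3, rho 0.76, SD of difference 2.29. Assumed for planning in section 2.1: SD of difference 3.0 for OLSA, and within-patient correlation 0.5 for the speech proportion. Month 3 variances, and correlations involving month 3, are not given. They are assumed below and varied.

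**The plan's own figures first.** SD of difference = √(2 × 3.3² × (1 − 0.76)) = √5.227 = 2.286, matching 2.29. Table 1 at n = 150 (mean difference 1.0, SD 3.0, noncentral t) gives power 0.98196, as stated. These figures concern the paired t-test and are not in dispute.

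**Formula.** For visits i and j, Var(i−j) = sᵢ² + sⱼ² − 2ρᵢⱼsᵢsⱼ. With complete data, the random-intercept model estimates the variance of every visit contrast as the mean of the three pairwise-difference variances. So, for 6 months minus pre-op:

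SE ratio (model/true) = √{[Var(3−0) + Var(6−0) + Var(6−3)] / [3 × Var(6−0)]}

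Approximate coverage of a nominal 95% interval = 2Φ(1.96 × ratio) − 1. The interval is too narrow only when Var(6−0) exceeds the mean of the three.

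**Central case (all inputs assumed):** SDs 20/22/22 at pre-op/month 3/month 6, pre/post correlation 0.3, month 3/6 correlation 0.85.
- Var(3−0) = Var(6−0) = 400 + 484 − 2 × 0.3 × 20 × 22 = 620
- Var(6−3) = 2 × 484 × 0.15 = 145.2
- Mean = (620 + 620 + 145.2)/3 = 461.7
- Ratio = √(461.7/620) = 0.863; coverage 90.9%

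**Range around it.** Post-op SDs 22, pre-op SD 15–25, pre/post correlation 0.2–0.5, month 3/6 correlation 0.75–0.90: ratio 0.838 to 0.938 (SE 6–16% too small), coverage 90.0–93.4%. For month 6 versus month 3 the model SE is 1.2 to 2.5 times too large.

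**Other patterns.** Correlations are listed as pre/3, pre/6, 3/6. Giving the SAP's 0.5 and 0.76 these roles is an assumption made here; the SAP does not do so.

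| SDs | Correlations | Ratio | Coverage |
|---|---|---|---|
| 3.3/3.3/3.3 | 0.76, 0.76, 0.76 | 1.00 | 95% |
| 3.3/3.3/3.3 | 0.5, 0.5, 0.76 | 0.909 | 92.5% |
| 3.3/3.3/3.3 | 0.76, 0.58, 0.76 | 0.844 | 90.2% |
| 20/6/6 | 0.2, 0.2, 0.7 | 0.828 | 89.5% |
| 10/25/25 | 0.5, 0.5, 0.76 | 0.937 | 93.4% |
| 10/25/25 | 0.5, 0.5, 0.5 | 1.051 | 96.1% |
| 3.3/4.5/3.3 | 0.5, 0.5, 0.5 | 1.154 | 97.6% |
| 3.3/4.5/3.3 | 0.5, 0.6, 0.6 | 1.211 | 98.2% |

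In the second row the 95% half-width at n = 150 is 0.48 dB where it should be 0.53 dB.

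**Check by simulation.** Random-intercept models fitted to 150 simulated datasets per scenario (n = 150 patients, complete data) gave mean SE ratios against the paired analysis of 1.00, 0.91 and 1.06 for the first, second and sixth rows. The formula gives 1.00, 0.909 and 1.051.

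**The case against.** The strongest reply is that the SAP never says patient is the only random effect or that residuals are independent with equal variance. A reader might infer that the wording forces compound symmetry. It does not: the structure is left open, and PROC MIXED also accepts a REPEATED statement. This stands as far as it goes, but an analyst following the text literally would fit the default, and nothing in the SAP points elsewhere.

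Second, a reader might infer that the 6-month interval must come out too narrow. The documents do not support that. They give no month 3 variance or correlation, and the table runs from 0.83 to 1.21. The too-wide cases need either a 3-to-6-month change that varies more than the pre-to-post change, or a month 3 SD well above the other two. These look less natural with the same implant at both visits, but they cannot be excluded.

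Third, the sentence requiring a patient random effect closes a block about GENMOD, GLIMMIX and a binomial response. The common-variance argument does not carry over directly to binary models, and GENMOD can use empirical standard errors. This stands, and the point is confined to continuous outcomes.

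Fourth, the device argument does not fit every outcome. Unaided thresholds involve no device at any visit, so there only the before-and-after-surgery contrast remains. Electrode impedances are measured on the implant and have no pre-op value. Both limits stand.

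Finally, residual diagnostics are planned. They could reveal unequal variances, but with no rule attached they settle nothing in advance.

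**Conclusion.** The point holds as a gap in specification with a probable direction. Read literally, the three-visit model for continuous outcomes assumes one variance and one correlation, which this design makes doubtful. If months 3 and 6 are more alike than either is with pre-op, at similar SDs, the 6-month versus pre-op SE is about 6–16% too small and nominal 95% intervals cover about 90–93%. Those sizes rest on assumed SDs and correlations and on complete data. Under other patterns the interval is correct or too wide.

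A reader might also infer that the main result is anti-conservative, with a type I error near 9% (the complement of the 90.9% in the central case). The documents do not support that. Primary hypothesis 1 is tested by a two-visit paired t-test, and neither that test nor the ANCOVA uses the pooled three-visit variance. The SAP itself ranks the ITT model as a sensitivity analysis, and it states no hypothesis for the thresholds. What is exposed is the ITT sensitivity model for continuous speech scores and the interval for secondary endpoint 1, which has no other stated inferential model.

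**What to change.** In SAP section 8.2, for continuous outcomes measured at all three visits, replace the patient random intercept with an unstructured within-patient covariance over visits (REPEATED visit / SUBJECT=patient TYPE=UN, with Kenward-Roger degrees of freedom). Keep 6 months minus pre-op as the contrast. With complete data its standard error then matches that of the paired analysis (ratio 1.00) in every scenario above, so nobody has to guess the covariance pattern beforehand.

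The cost is one SAP sentence and one line of code. The model estimates six covariance parameters instead of two, which is readily done with 150 patients. Intervals for the 6-month contrast may be slightly wider. The paired t-test, the ANCOVA and the binary-response models need no change on this account.

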9 SAFETY ANALYSIS

Not applicable as no specific safety analyses are planned.
